3.1.3. G03-52-01 Development

G03-52-01 drug product (DP) is being investigated for pre-exposure and post-exposure prophylaxis of botulism from BoNT/A and/or BoNT/B in adults. G03-52-01 is a mixture of five human immunoglobulin G (IgG)1 antibodies and one humanized IgG1 antibody each with distinct specificities that are individually expressed in a Chinese hamster ovary (CHO) cell line. Each of the drug substance antibodies (anti-BoNT/A NX01, NX02, NX11 and anti-BoNT/B XB10, XB18, XB23) used in the manufacture of G03-52-01 binds non-overlapping regions on BoNT/A or BoNT/B. While each of the monoclonal antibodies (mAbs) binds to a distinct epitope on BoNT/A or BoNT/B, none was able to sufficiently neutralize BoNT when tested alone *in vivo*. The *in vivo* studies showed that the highest levels of mAb potency were dependent on the presence of three antibodies.¹⁵ The protective capacity of G03-52-01 to neutralize toxicity caused by BoNT/A and BoNT/B has been verified in mice and in guinea pigs.

As these DPs are directed at foreign targets not expressed in animals or humans and based on the observed lack of cross-reactivity of G03-52-01 in healthy human and animal tissue, the focus of the nonclinical safety evaluation of G03-52-01 was to assess potential off-target toxicity and to identify any untoward effects due to administration of either DP.

A Good Laboratory Practice (GLP) 12-week repeat dose toxicity study was performed to evaluate the safety of G03-52-01 in rats when administered by intramuscular (IM) injection once weekly for three injections and to evaluate toxicity and reversibility of effects after a two-month recovery period. The study consisted of four Main Study/Recovery dose groups (15 rats/sex/group) and four Toxicokinetic (TK) dose groups (12 rats/sex/group). Experimental endpoints included moribundity/mortality; physical examinations (PEs), injection site (Draize) reactogenicity scoring; body weights; food consumption; body temperature measurements; clinical pathology parameters (clinical chemistry, hematology, and coagulation); serum drug levels/TKs; organ weights; gross pathology at necropsy; and microscopic pathology. IM treatment at doses of 10, 50, or 100 mg/kg of G03-52-01 against BoNTs A and B did not result in any treatment-related, toxicologically significant, or adverse findings following three injections on Study Days 1, 8, and 15. Therefore, the No Observed Adverse Effect Level (NOAEL) was 100 mg/kg for this study.

The safety and pharmacokinetics (PK) of G03-52-01 were evaluated in a Phase 1 clinical study of a single IM injection of G03-52-01 conducted by Resilience Government Services (RGS). There were no safety concerns with the administration of the DP. All subjects in Cohorts 1-3 of the Phase 2 clinical study completed their last subject visit. All available safety data was reviewed by the DSMB and no safety concerns were identified.

3.2. Rationale For Use of G03-52-01

BoNTs considered the most potent biologic toxins known and are classified as a Category A bioterrorist with BoNT/A most likely to be used in this scenario. Military biological warfare can weaponize, produce, and disperse aerosols of manufactured purified botulinum toxins with the intent of inhalational exposures.⁴ The lethal doses for purified crystalline botulinum toxin type A for a 154-lb (70-kg) man are estimated to be 70 µg when introduced orally and 0.80–0.90 µg when inhaled.^{16, 17, 18} Considering the increase in medicinal use, legalized and illicit manufacturing, and limited availability for prophylaxis and treatment options, the serious threat for protecting at-risk military personnel remains.

Two polyclonal antisera-based products are available for the treatment of botulism, BAT® and BabyBIG®. The BAT and BabyBIG polyclonal antisera to treat botulism are made by hyperimmunizing either horses or human volunteers, respectively. Equine and human polyclonal antisera are not easily produced or scaled up, carry infectious agent risks, and differ from lot-to-lot production. The development of mAbs represents an alternative that can be produced at larger scale and with high quality

Based on nonclinical and clinical experience with other anti-BoNT mAbs, use of G03-52-01 for the prophylaxis and treatment of inhalation botulism from serotypes A and B in adults may provide the following advantages over the equine antitoxins:

- An improved safety profile:
 - Substantially decreased anaphylaxis and no risk of serum sickness
 - G03-52-01 is directed at foreign targets not expressed in animals or humans
 - Toxicity studies demonstrated a lack of cross-reactivity of G03-52-01 in healthy human tissue
- A longer half-life
- The ability to administer repeated doses for prevention and therapy
- The ability to use small doses via IV and IM administration (permitting flexible administration scenarios, including self-administration)
- The ability to easily and consistently manufacture a large number of doses in sufficient quantities for stockpiling

The Phase 1 clinical trial evaluated the safety and tolerability of a single IM injection of G03-52-01 administered to healthy adults. Sentinel dosing occurred within each cohort as described in the full protocol (G03-52-001.001). The starting dose in the clinical trial was 10 mg, which was escalated to 25 mg, 50 mg, and 100 mg with no safety concerns identified. G03-52-01 was safe and well tolerated in all subjects who participated in the Phase 1 study and in the Phase 2 study to date.

The nonclinical Investigational New Drug (IND)-enabling toxicology studies were designed to support this clinical design, including the dose levels and IM route of administration. Based on the potency of the G03-52-01 lots manufactured to date, the doses evaluated are anticipated to support PK analyses with serum drug concentrations in the range for pre-exposure and post-exposure prophylaxis of botulism from BoNT/A and BoNT/B.

3.3. Potential Risks and Benefits

3.3.1. Potential Risks

The potential risks to the subjects due to participation in the study are those related to venipuncture, the IM injection and the administration of G03-52-01.

Venipuncture

Venipuncture causes transient discomfort and may cause fainting. Bruising at the site of the venipuncture may occur but can be prevented or lessened by applying pressure for several minutes. Infection at the site is possible but highly unlikely as aseptic technique must be employed.

IM Injection

An IM injection may cause some discomfort at the injection site. Other risks may include pain, redness, swelling, or warmth at the injection site. These risks are minimal.

G03-52-01

No safety concerns or risks associated with G03-52-01 were indicated during a Phase 1 study.

Risk Factors Associated with Monoclonal Antibodies

Injections of mAbs may be associated with injection reactions including anaphylaxis/anaphylactoid type reaction, especially during a first exposure, and when administered rapidly. Fever, chills and rigors, typically occurring within the first two hours following injection, characterize these reactions. Other symptoms sometimes associated with injection reactions include nausea, vomiting, rash, pruritus, bronchospasm or other acute pulmonary response, angioedema, hypotension, hypertension, cardiac arrhythmias, dizziness, dyspnea, headache, and malaise.

Risk of Immunogenicity

Antibodies directed against G03-52-01 may develop following injection. This will be assessed by taking blood samples at selected visits throughout the study. G03-52-01 is a fully humanized mAb which based on experience with other humanized or chimeric mAbs, reduces the immunogenic potential.

3.3.2. Known Potential Benefits

This trial has no benefit for the subjects participating in the trial. The knowledge gained in this trial may help society, especially those exposed to, or at risk of being exposed to, the toxins of botulism.

4. OBJECTIVES

4.1. Study Objectives

Primary Objective:

- To evaluate the safety and tolerability of single or repeat IM administration of G03-52-01 in health adult subjects
- For Cohorts 1-3
 - Demonstrate target protective concentration (NAC) value > 0.02 U/mL (BoNT/A) or > 0.03 U/mL (BoNT/B) at Day 45 and Day 90
 - To evaluate lot-to-lot variability of two doses of G03-52-01
- For Cohort 4, demonstrate target protective concentration (NAC) value of BoNT/A and BoNT/B at 4 and 8 hours post dose

Secondary Objective:

- Cohorts 1-3
 - Demonstrate target protective concentration (NAC) value > 0.02 U/mL (BoNT/A) or > 0.03 U/mL (BoNT/B) at Day 120
 - To evaluate pharmacodynamic (PD) and anti-drug antibody (ADA) at pre-dose through the end of study
- Cohort 4
 - Demonstrate target protective concentration (NAC) value of BoNT/A and BoNT/B at 2 hours post dose
 - To assess pharmacokinetics (PK) at pre-dose through end of study
 - To evaluate pharmacodynamic (PD) and anti-drug antibody (ADA) at pre-dose through the end of study

Exploratory Objectives:

- For Cohorts 1-3, to evaluate PK parameters to ensure ADA evaluation adequate of the two lots

4.2. Study Outcome Measures

4.2.1. Primary Endpoints

- The occurrence of adverse events (AEs) and serious adverse events (SAEs) following administration of G03-52-01 to the final visit
- The occurrence of changes from baseline in PE, vital signs, and clinical safety laboratory values following administration of G03-52-01 to the final follow-up visit

- For Cohorts 1-3, to evaluate the proportion of subjects with target protective concentration (NAC) value > 0.02 U/mL (BoNT/A) or > 0.03 U/mL (BoNT/B) at Day 45 and Day 90
- For Cohort 4, to evaluate the proportion of subjects with target protective concentration (NAC) value > 0.02 U/mL (botulinum neurotoxin [BoNT]/A) or > 0.03 U/mL (BoNT/B) at 4 and 8 hours post dose

4.2.2. Secondary Endpoints

- Cohorts 1-3
 - To evaluate the proportion of subjects with target protective concentration (NAC) value > 0.02 U/mL (BoNT/A) or > 0.03 U/mL (BoNT/B) at Day 120
 - Descriptive statistics of selected PD and ADA at all timepoints tested
- Cohort 4
 - To evaluate the proportion of subjects with target protective concentration (NAC) value > 0.02 U/mL (botulinum neurotoxin [BoNT]/A) or > 0.03 U/mL (BoNT/B) at 2 hours post dose
 - PK analysis at the determined timepoints
 - Descriptive statistics of determined PD and ADA timepoints

4.2.3. Exploratory Endpoints

- For Cohorts 1-3, descriptive statistics of selected PK parameters at all time points tested of the two lots

5. INVESTIGATIONAL PLAN

5.1. Study Design

This is a Phase 2, multicenter, randomized, double-blinded, placebo-controlled study to evaluate the safety, tolerability, pharmacodynamics (PD), and immunogenicity of a single dose (100 mg) and a repeat dose (50 mg and 100 mg) of G03-52-01 administered by IM injection(s) in adult subjects ([Appendix C](#)).

Approximately 625 subjects will be enrolled in this study to receive active product or placebo on Day 1 or Day 1 and Day 45, and will be randomized to the following concurrent cohorts:

- Cohort 1 (N=150, 75 lot #1, 75 lot #2): 50-mg dose
- Cohort 2 (N=150, 75 lot#1, 75 lot#2): 100-mg dose
- Cohort 3 (N=75): Placebo
- Cohort 4 (N=250): 100 mg dose or Placebo

The study will include up to 14-day screening period and an approximately 1-hour stay for Cohorts 1-3 and 8 hours stay for Cohort 4 in the clinic after dosing is complete for PK assessment and to ensure that no hypersensitivities or safety signals occur. Follow-up visits will occur at 24 hours and 72 hours post dose, and on Days 8, 15, 45, 49, 60, 90, 120, 150, 180, and 240 for Cohorts 1-3. For Cohort 4, follow-up visits will occur 24 hours, 72 hours, and on Days 8, 15, 30, 45, 90, and 120.

Safety Analysis

Safety labs will be drawn at pre-dose, 24 hours post dose, and on Days 15, 45 (before repeat-dose or placebo), 60, 120, and 240 for Cohort 1-3. Subjects in Cohort 4 will have safety labs drawn at screening and on Day 15, 45, and 120.

PD Analysis

PD samples will be collected for all subjects. Analysis will be completed by the Battelle Mouse Neutralization Assay (MNA) for Serotypes A and B.

Samples for subjects in Cohorts 1-3 will be tested at pre-dose, 24 hours post dose, and on Days 8, 15, 45 (before repeat-dose or placebo), 49, 90, and 120. The first 25 subjects randomized for each DP lot of 50 mg and 100 mg doses and placebo will be tested at all 8 timepoints. The remaining samples from the subjects who received either dose or lot of G03-52-01 (including placebo) will only be tested using MNA at pre-dose and Days 45, 90, and 120.

All subjects in Cohort 4 will have samples collected at pre-dose, 2 hours, 4 hours, 8 hours, 24 hours and on Days 30, 45, and 90. Samples will be analyzed for the first 30 subjects in Cohort 4, who receive active drug and complete the sample collection at 24 hours. See [Figure 2](#) and [Figure 3](#).

PK Analysis

PK samples will be collected for all subjects. Analysis will be completed by electrochemiluminescence assay (ECLA) or enzyme-linked immunosorbent assay (ELISA).

Samples for subjects in Cohorts 1-3 will be tested at pre-dose, 24 hours and 72 hours post-dose, and on Days 8, 15, 45 (before repeat-dose or placebo), 49, 90, and 120. The first 25 subjects randomized for each DP lot of 50 mg and 100 mg doses and placebo will be tested at all timepoints.

All subjects in Cohort 4 will have samples collected at pre-dose, 2 hour, 4 hours, 8 hours, 24 hours, 72 hours post dose, and on Days 8, 15, 30, 45, 90, and 120. Samples will be analyzed for the first 30 subjects in Cohort 4, who receive active drug and complete sample collection at 24 hours. See [Figure 2](#) and [Figure 3](#).

ADA Analysis

ADA will be evaluated by ECLA at pre-dose and on Days 15, 45 (before repeat-dose or placebo), 60, 90, 120, 150, 180, and 240 for study subjects in Cohorts 1-3; and at pre-dose and post dose on Days 90 and 120 for subjects in Cohort 4. See [Figure 2](#) and [Figure 3](#).

Figure 2: Cohort 4 Assessments

[figure not shown]
[figure not shown]

Figure 3: Study Design

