PD samples will be tested by the Battelle Mouse Neutralization Assay (MNA) for serotypes A and B at pre-dose, 24 hours post dose, and on Days 8, 15, 45 (before repeat-dose), 49, 90, and 120. The first 25 subjects randomized for each drug product (DP) lot of 50 mg and 100 mg doses and placebo will be tested at all 8 timepoints. The remaining samples from the subjects who received either dose or lot of G03-52-01 (including placebo) will only be tested using MNA at pre-dose and Days 45, 90, and 120.

PK samples will be tested by electrochemiluminescence assay (ECLA) or enzyme-linked immunosorbent assay (ELISA) at pre-dose, 24 hours and 72 hours post dose, and on Days 8, 15, 45 (before repeat-dose), 49, 90, and 120. A total of 25 subjects for each DP lot of 50 mg and 100 mg doses and placebo will be tested at all timepoints.

For Cohort 4, PK and PD samples will be tested for the first 30 subjects who receive active drug and complete sample collection at 24 hours. PD samples will be tested by the Battelle Mouse Neutralization Assay (MNA) for serotypes A and B at pre-dose, 2 hours, 4 hours, 8 hours, 24 hours and on Days 30, and 45 and 90. PK samples will be tested by electrochemiluminescence assay (ECLA) or enzyme-linked immunosorbent assay (ELISA) at pre-dose, 2 hours, 4 hours, 8 hours, 24 hours, 72 hours post dose, and on Days 8, 15, 30, 45, 90, and 120.

ADA samples will be tested at pre-dose and Days 15, 45 (before repeat-dose or placebo), 60, 90, 120, 150, 180, and 240 for study subjects in Cohorts 1-3; and at pre-dose and post-dose on Days 90 and 120 for Cohort 4.

An interim Clinical Study Report (CSR) is planned for the first 125 subjects in Cohorts 1-3 through Day 120.

Study Population:

625 healthy male and female subjects between the ages of 18 and 65 years of age

Inclusion Criteria:

1. Informed consent understood and signed prior to screening procedures.

2. Assessed by the Investigator to be a healthy male or healthy, non-pregnant, non-lactating female between the ages of 18 and 65 inclusive on the day of dosing.
3. Able and willing to comply and be available for all protocol procedures and follow-up for the duration of the study.
4. Body Mass Index (BMI) of ≥ 18.5 and ≤ 35 kg/m².
5. Females of child-bearing potential must have a negative serum pregnancy test at screening and negative urine pregnancy test on Day 1 prior to dosing.

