5.4.2. Randomization Procedures

Randomized treatment assignments will be generated by centralized randomization system. The system will be used each day that a subject, who has been screened and qualified at the site, returns for a study visit. Subjects will be randomized 2:2:1 to the following concurrent cohorts:

- Cohort 1: 50-mg dose of G03-52-01 on Day 1 and repeat 50-mg dose on Day 45 (N=150)
- Cohort 2: 100-mg dose of G03-52-01 on Day 1 and repeat 100-mg dose on Day 45 (N=150)
- Cohort 3: Placebo on Day 1 and placebo on Day 45 (N=75)

Within Cohorts 1 and 2, subjects will be randomized 1:1 to receive their study drug from Lots 1 or 2 of the drug. Within each of the 4 study drug dose/lots and the placebo cohort, subjects will be randomized 2:1 to provide PD or PK specimens at visits specified in the Schedule of Assessments ([Appendix A](#)).

Subjects in Cohort 4 will be randomized in a 4:1 to receive a single 100-mg dose of G03-52-01 or Placebo on Day 1 (N=250).

All individuals with access to study subjects or subject data will remain blinded until all data are entered and verified, and database is locked.

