11.2. Planned Interim Analysis

An interim Clinical Study Report (CSR) is planned for the first 125 subjects across the first three cohorts through Day 120. The data cut will be taken when all 125 subjects have completed their Day 120 visit for PD, PK, and ADA analysis. All available safety from subjects in Cohorts 1-3 will be included until the data cutoff for the DSMB report. The objectives of this interim CSR will be to compare safety between the 3 cohorts and to evaluate lot-to-lot variation in PK, PD and immunogenicity parameters within drug dose levels as defined in the SAP.

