### 3.3 Randomization and Blinding

For Cohorts 1-3, eligible subjects will be randomized to one of the 5 parallel treatment groups (50 mg G03-52-01 Lots 1 and 2, 100mg G03-52-01 Lots 1 and 2, and Placebo) in a 1:1:1:1:1 ratio, respectively, via the centralized randomization using Interactive Response Technology (IRT) randomization system (Table 1). Cohort 1-3 subjects will receive one dose of either G03-52-01 or Placebo on Days 1 and 45 for a total of two doses. No stratification will be performed for randomization.

For Cohort 4, eligible subjects will be randomized into one of 2 treatment groups (100 mg G03-52-01 or Placebo) in a 4:1 ratio. Cohort 4 subjects will receive one dose of either G03-52-01 or Placebo on Day 1. No stratification will be performed for randomization.

The ICON Randomization Development Team will generate the randomization schedule according to the sponsor protocol number G03-52-01-002, V4.0, 14Apr2024. The ICON team will deliver dummy and live randomization schedules to the IVRS System Development Team via a password-protected .zip file sent through e-mail.

The study staff participating in the administration of study product and assessment of the subjects and the subjects will be refrained from understanding the contents of the IM vial and are blinded from the study product information. Please refer to the Cohorts 1-3 Randomization Plan, v1.0, 16May2022 and Cohort 4 Randomization Plan, v1.0, 18Apr2024 for the detailed randomization list preparation and implementation.

The Investigator may unblind a subject's treatment assignment only in the case of an emergency or a serious adverse event (SAE) when knowledge of the study treatment is essential to the appropriate clinical management or welfare of the subject. Whenever possible, the Investigator should first discuss the options

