Vital sign assessments will be performed at all in-clinic study visits, including systolic and diastolic blood pressure (BP), heart rate (HR), and oral temperature. During screening and follow-up, a measurement that is a Grade 1 (as referenced in Protocol G03-52-01-002, v4.0, 14Apr2024, Appendix B) may be repeated once if the principal investigator believes a transient condition led to the aberrant value. Vital signs obtained at screening will serve as baseline values for the subject. Grade 1 values are allowable unless deemed clinically significant by the study Investigator.

- **Electrocardiogram (ECG)**

A 12-lead ECG will be performed at screening and reviewed by the study PI or a co-Investigator to assess the cardiac status of a subject for eligibility for enrollment.

- **Laboratory Evaluations**

Laboratory assessment schedule will follow the Schedule of Assessments in Appendix A. Detailed laboratory tests can be found in Section 8.5.2 of Protocol G03-52-01-002, v4.0, 14Apr2024.

- **Pharmacodynamic (PD) and Pharmacokinetic (PK) Assays**

Blood samples for PD assessment will be collected at pre-dose, 24 hours post-dose, and on Days 8, 15, 45 (prior to dosing) 49, 90, and 120 for all subjects in Cohorts 1-3. The first 25 subjects randomized for each DP lot of 50 mg and 100 mg doses and placebo will be tested at all 8 timepoints. The remaining samples from the subjects who received either dose or lot of G03-52-01 (including placebo) will only be tested using MNA at pre-dose and Days 45, 90, and 120.

Blood samples for PD assessment will be collected at pre-dose, 2 hours, 4 hours, 8 hours, 24 hours, and on Days 30, 45, and 90 for all subjects in Cohort 4. Cohort 4 samples for the first 30 subjects, who receive active drug product and complete sample collection at 24 hours, will be tested at pre-dose, 2 hours, 4 hours, 8 hours, 24 hours, and on Days 30, 45, and 90. PD samples will be analyzed for neutralizing antibody concentration (NAC) using the validated Battelle MNA.

Blood samples for PK assessment will be collected at pre-dose, 24 hours and 72 hours post-dose, and on Days 8, 15, 45 (prior to dosing), 49, 90, and 120 for all subjects in Cohorts 1-3. The first 25 subjects randomized for each DP lot of 50 mg and 100 mg doses and placebo will be tested at all timepoints.

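### Cohort 4's primary 4-hour and 8-hour NAC rate rests on the first 30 active subjects by enrolment order; a random 30 would remove that selection with no extra assays

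*Protocol*

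**What the plan says.** - **Endpoint.** Protocol 4.2.1 makes this a primary endpoint: "For Cohort 4, to evaluate the proportion of subjects with target protective concentration (NAC) value" above 0.02 U/mL (BoNT/A) or 0.03 U/mL (BoNT/B) at 4 and 8 hours. SAP 9.10.4 reports it for active drug as a count and percentage of subjects with evaluable concentrations at the time point.
- **Who is sampled.** Protocol 5.1: "All subjects in Cohort 4 will have samples collected at pre-dose, 2 hours, 4 hours, 8 hours, 24 hours", and at later visits.
- **Who is assayed.** Protocol 5.1: "Samples will be analyzed for the first 30 subjects in Cohort 4, who receive active drug and complete the sample collection at 24 hours". The synopsis and Protocol 8.6.1 and 8.6.2 give the same rule. SAP 3.4 agrees: "Cohort 4 samples for the first 30 subjects, who receive active drug product and complete sample collection at 24 hours, will be tested". Neither document says why the earliest subjects are used, or why there are 30.
- **When results are needed.** Protocol 11.2: "An interim Clinical Study Report (CSR) is planned for the first 125 subjects across the first three cohorts through Day 120". SAP 4.1 likewise limits the interim analysis to Cohorts 1-3. SAP 4.2 plans one DSMB meeting for Cohort 4, and the data it lists are safety, disposition, subject characteristics and deviations, not NAC. SAP 4.3 puts the final analyses after database lock.
- **Cohorts 1-3 for contrast.** Under Protocol 5.1 the first 25 per lot (and placebo) get the full eight-point PD profile, but the remaining subjects are still tested pre-dose and at Days 45, 90 and 120. The early-enrolment rule there does not confine the primary time points to early subjects. Protocol 5.4.2 also already uses randomisation (2:1) to decide which Cohort 1-3 subjects provide PD or PK specimens.

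**The concern.** In Cohort 4 the early-enrolment rule decides who enters the primary NAC estimate at all; no later active subject can contribute. The result will be read as the rate for the Cohort 4 active group, and Cohort 4 uses its own drug product lot (Protocol 7.3), so these 30 are the only planned NAC data on that lot. A fixed 100 mg dose is given across a BMI range of 18.5 to 35. If weight mix, injection practice or sample timing changes as enrolment proceeds, the change goes straight into the primary estimate. A binomial interval on 30 subjects does not allow for it. The plan gains nothing it states by taking the earliest subjects, and the samples needed for a random choice are collected anyway.

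**Working it through.** **Inputs**
- Cohort 4: 250 subjects at 4:1 (Protocol 5.4.2). SAP 3.1 states 200 active and 50 placebo.
- Assayed: 30 active (Protocol 5.1, SAP 3.4).
- Early-versus-late difference d: not in the documents. Assumed at 5, 10 and 20 percentage points.

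**1. The plan's own figure.** 250 × 4/5 = 200 active and 250 × 1/5 = 50 placebo. This matches SAP 3.1. The 30 has no stated derivation to reproduce.

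**2. Share assayed.** 30/200 = 15%, so 170/200 = 85% of active subjects are not assayed for NAC. Thirty active subjects are expected after 30/0.8 = 37.5 randomisations, which is 37.5/250 = 15% of Cohort 4 enrolment (more if some miss the 24-hour collection).

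**3. Selection bias of the first 30.** Let p_E be the rate in the first 30, p_L the rate in the other 170, and d = p_E − p_L.
- Rate in all 200: p = (30 p_E + 170 p_L)/200 = 0.15 p_E + 0.85 p_L.
- Bias: p_E − p = 0.85 (p_E − p_L) = 0.85 d.

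| Assumed d (points) | Bias against all 200 (points) |
|---|---|
| 5 | 4.25, about 4.3 |
| 10 | 8.5 |
| 20 | 17 |

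Example: with 30/30 above target early and 90% among the other 170, the cohort rate is 0.15 × 100 + 0.85 × 90 = 91.5%, against a reported 100%.

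**4. A random 30.** Each active subject has the same 15% chance of selection, so the expected selection bias is 0 whatever d is.

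**5. Precision.** Exact (Clopper-Pearson) 95% intervals depend only on the count and n. For n/n the lower limit is 0.025^(1/n); at n = 30 it is 88.4%.

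| Result | 95% interval |
|---|---|
| 30/30 | 88.4 to 100% |
| 27/30 | 73.5 to 97.9% |
| 24/30 | 61.4 to 92.3% |
| 200/200 | 98.2 to 100% |
| 180/200 | 85.0 to 93.8% |

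The first three rows hold for the first 30 and for a random 30 alike. Only more assays narrow the interval. At 27/30 the lower arm is 90 − 73.5 = 16.5 points, so biases of 4.3 or 8.5 sit inside ordinary sampling error at this n, and 17 is just outside it.

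**The case against.** **The documents do not show that early subjects differ.** This stands. All are healthy volunteers under one set of criteria, on one dose from one lot, and d is assumed throughout. By Protocol 3.1.3 all Cohort 1-3 subjects had finished their visits; if the same sites took part in Cohort 4, which is not stated, its start was not their first use of the product.

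**The consequences are limited.** This also stands. There is no hypothesis test, power claim or success threshold. SAP 9.10.4 asks only for counts and percentages, and the rule is prespecified in both documents. The NAC rate is reported for active drug alone, so no treatment comparison is biased.

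Three stronger readings are tempting but unsupported:
- *The 30 will come from two or three early sites, so the effective sample size is well below 30.* SAP 3.3 says "No stratification will be performed for randomization", but stratifying allocation balances arms within sites and does not decide which sites enrol first. The approximately 15 sites in the synopsis are for the whole study; the number of Cohort 4 sites and their opening order are not given. If 15 sites opened together, 37.5 randomised subjects would be 2.5 per site, or 30/15 = 2 active each. The documents support no design effect.
- *The 24-hour condition spoils the primary endpoint.* It does select on an event after the 4- and 8-hour samples. But the same 30 supply the PK and PD profiles, for which early completeness is useful, and a subject who misses the visit is replaced by the next. No missed-visit rate is given, and the effect is probably small.
- *Samples from all 250 subjects are stored and waiting.* The text says collected. Future-use storage in Protocol 8.6.4 covers Cohorts 1-3 only, and Protocol 8.6.5 leaves storage to the Laboratory Manual.

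Taking the first 30 is also objective and leaves no discretion. So does a draw fixed in advance by a random seed. An unstated operational reason, such as assay scheduling, cannot be excluded.

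**Conclusion.** The concern holds as a cheap improvement, not as an error. The Cohort 4 primary NAC rate at 4 and 8 hours, and the 2-hour NAC, PK and PD summaries, come from 15% of the active group chosen by enrolment order, with no stated need for early results. The resulting bias is 0.85 × d. Its size rests wholly on an assumed d and could be zero. The calculation takes the planned 200 active subjects as the pool and ignores those with incomplete collection. Random selection would make the estimate representative in expectation at the same n; it would not make it more precise.

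**What to change.** In the protocol synopsis, Protocol 5.1, 8.6.1 and 8.6.2, and SAP 3.4, replace the first-30 rule with a random sample of 30 active subjects, allocated in proportion to site enrolment, drawn by the unblinded statistician from those with complete 2-, 4-, 8- and 24-hour collection. This keeps the completeness that the 2-hour NAC, PK and PD profiles need. Either timing works:
- draw after Cohort 4 enrolment closes, which allows exact allocation by site; or
- put a random flag in the randomisation list beforehand, with a preset order of replacements, so that assays can start during enrolment. Site proportions then hold only on average.

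**Cost.** Wording in both documents. The assay count, visits and blood draws are unchanged. Picking 30 active subjects needs access to the treatment code under either rule, so no new unblinding arises. The downside is later or more spread-out assay runs; check first that the Laboratory Manual's storage stability allows it.

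**If the first 30 have already been assayed**, which the documents do not say, label the estimate in the SAP and the report as an early-enrolment subset, and tabulate site, weight and BMI of the 30 against the remaining active subjects.
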